The study staff will provide \$100 gift card compensation to all participants attending the baseline interview and complete the protocols. Since this is the last procedure, the participant will be involved with for this visit, the study staff will provide an envelope to the participant. The envelope will be labeled with the name of the study, the research coordinator's name and contact number. In the envelope the participant will locate two Ziploc baggies, 1 for each worn sensor. Each baggie will be labeled as "sensor 1" and "sensor 2;" the baggie will also contain one of the stickers designated for each sensor (these stickers will be found within the Dexcom G6 Pro kit box). The study staff will explain to the participant that the bag labeled "Sensor 1" is for them to put in the sensor that has been recently applied on the 10th day and the bag labeled "Sensor 2" is designated for the 2nd sensor they will apply on their own once they have completed the 20 days (about 3 weeks) of the CGM phase.

Data entry

The study staff will ensure to transfer the baseline data collected from the participant's chart into the RC system on the same day as the baseline visit. This will ensure that the main data capture system remains up to date.

CGM Wear Phase

The CGM wear phase will span 20 consecutive days. Throughout this period, we will gather data from the participants on a weekly basis. The sensor will be replaced once on day 10. Each morning, participants will receive text prompts to log dietary behaviors that triggered high out-of-range alarms; these logs will be recorded directly in the app by the participant. During the Zoom-supported sensor replacement call, the staff will replace the sensor and inquire about any adverse events or serious adverse events related to the sensor. Additionally, study staff will conduct Zoom sessions with participants on the 10th day of wearing transmitters during the CGM phase.

Dietary logs

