The research staff will send a text message to the participant to remind them the date and time they scheduled the sensor replacement 48h before the sensor replacement. The research staff will conduct a Zoom phone call with each participant on day 10 to assist with sensor replacement. The replacement Zoom will be scheduled during the baseline visit. Additionally, participants will be asked about any adverse events related to the CGM sensor as listed on the RC survey form, including inputting AE and SAE. Three days before the scheduled call, the research staff will send each participant a G6-Pro application video tutorial. On the 10th day of wearing the CGM, the research staff will meet with participants via Zoom to guide them through the process of changing the G6-Pro sensor. During this meeting, the research staff will provide a step-by-step explanation of the sensor replacement procedure, allowing participants to ask any questions they may have and receive support from the research team. Participants will be reminded not to discard the used transmitter-sensor; instead, they will be instructed to place it in the envelope provided by the research staff during the baseline visit.

Before the zoom call takes place, the study staff will login into their RC account and select the G1-Study project to be able to access the participants' charts of the G1-Study. After the website takes the staff to the study page, the staff will select the tab called "Record Status Dashboard" found on the left hand of their screen. The platform will then show the list of each participant and with each form/survey involved in each phase of the study. For this activity, the study staff will choose the only survey found on the "CGM Phase" column. The study staff will have this survey open throughout the zoom call and will complete the form after the participant has successfully removed the old sensor and replaced the new G6 PRO sensor. An example of the Sensor Replacement Telephone script is provided in the Appendix _H_.

Compensation

For the CGM phase, each participant will receive \$200 compensation, which will be given as gift cards. The first \$100 gift card is assigned to the first 7-10 days of successful wear, and \$100 is applied to the second 7-10 days of wear after replacement. Both gift cards are given to the participant at their post visit.

Post-Visit

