APPENDIX H: SENSOR REPLACEMENT TELEPHONE SCRIPT

"Hello Mr./Mrs._____,

Thank you for joining me on this call. How are you doing today?

I am so glad to hear that. As we discussed during your Baseline Visit, we scheduled this call for 2 main reasons.

One reason is that the sensor that you applied during the BV expires on this day, therefore, you must remove it and replace it with a new Dexcom sensor on this day.

I am also going to guide you through the entire procedure of your sensor replacement.

I want to remind you that your participation in this study is completely voluntary. Would you still like to continue with your participation in this phase of the study?

[After the participant agrees to continue with their participation]

Excellent! Before we start with the entire process, I want to show you a short video that will help you gain more knowledge about the Dexcom sensor application.

[The study staff will share the video by sharing their screen on the Zoom platform. The video shown will be the following: <https://www.youtube.com/watch?v=dWWKa3Fjd9Y> from minute 1:44 until minute 3:17]

Now that we have watched the video, do you have any questions regarding the sensor application?

[Study staff will address every question that the participant has at that moment]

Excellent Mr./Mrs._____ We will now start the process of removing and replacing your sensor. I will show you the supplies you will need for these activities.

[Study staff will show on screen the following: manila envelope, labeled Ziploc baggies found within the envelope; Dexcom G6 PRO box containing the applicator with the sensor, the 2 alcohol pads, and the transmitter]

Do you have this equipment on hand?

[If not, give time to the participant to gather every equipment needed for the procedures. Make the participant show on their screen all their equipment]

We will now start by removing your sensor. Localize your sensor, pick one of the corners of the sensor's adhesive, and start gently peeling off the adhesive as if you are peeling off a band-aid.

[After the participant removes the sensor, tell the participant to show you on screen the removed sensor]

Great job on removing your sensor Mr./Mrs._____, now please grab one of the Ziploc baggies found within the envelope labeled -Sensor 1- and place the worn sensor in the Ziploc baggie, then place the Ziploc baggie inside the manila envelope.

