[Ask the participant if they have inserted the transmitter, if so, ask if the transmitter made a clicking noise]

Now that you have successfully inserted the transmitter, rub the sides of the adhesive with circular motions. Rub it at least 4 times.

Great job Mr./Mrs. _____, you have successfully applied your new sensor. Let’s now start to pair your new sensor with your smartphone. Unlock your smartphone and go into the Dexcom G6 App. Within your App, touch the settings icon found in the upper right-side corner of your screen

[Show on screen to the participant the settings icon of the app].

Now touch the fifth tab called “Transmitter”. You will see a section called “Pair New” on your screen.

[Show once again to the participant on screen the Pair New section]

Select that tab and hit the “continue” tab. The app will give you the option to either enter the Transmitter Code manually or scan the QR code. I’d like you to choose the QR code option. The app will open the camera so you can capture the QR code found on the sheet I mentioned at the beginning containing the sensor’s code.

[Show on screen once again the sheet with the QR code].

After you scan the code, the app will automatically pair your new sensor with your smartphone. The sensor will take up to 2 hours to warm up. After the 2 hours have passed, the G6 app will show you your glucose levels graph.

Amazing job, Mr./Mrs. _____. You successfully replaced and paired your new Dexcom G6 PRO sensor. We will now finish this zoom call with a short survey. Are you okay if we complete this now or do you need to take a 3-minute break?

[Once the participant has accepted to go on with the survey, the staff will go into the RC page that was set up from the beginning of the zoom meeting and will enter the correct data into the RC platform. Within this survey the study staff will schedule the date and time of the Post Visit. After finishing the survey, the staff will answer the participant’s questions and will thank them for their participation]

Thank you so much for participating in this phase of the study. Remember that if you have any problems with your sensor or the Dexcom app, feel free to contact me so I can help you solve the problem.

Before we go, I want to kindly remind you to continue making the daily videoclips so we can capture your entire experience with the glucose sensor."

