APPENDIX Q: SENSOR REPLACEMENT CALL SURVEY

Page 3

Did the call take place with the participant? Yes No

Insert the date that the sensor was replaced: _____

Sensor ID code of the replacement sensor: _____

Is the Dexcom Glucose kit complete with all its components? Yes No

How many days have you worn your CGM since we put it on? _____

Have you experienced any problems with your glucose monitoring system (sensor or app)? Yes No

Insert notes for sensor problems, smartphone app problems, and adverse events. _____

Was the sensor successfully replaced? [Have the participant show you their smartphone screen to verify working order] Yes No

En que lugar almaceno su segundo sensor? _____

Insert any additional notes related to this phone interview that impact the participant or data capture. _____

Other notes: _____

Upcoming visit date: _____

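### On the day-10 call, the explicit adverse-event question comes after the second sensor is applied and paired, and no scripted check precedes reapplication

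*Protocol*

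**What the plan says.** Protocol section 3.13.2 describes the day-10 contact twice. Under CGM Wear Phase, "the staff will replace the sensor and inquire about any adverse events or serious adverse events related to the sensor". Under G6 sensor replacement, "participants will be asked about any adverse events related to the CGM sensor as listed on the RC survey form, including inputting AE and SAE". The latter subsection adds that staff keep the form open during the call and "will complete the form after the participant has successfully removed the old sensor and replaced the new G6 PRO sensor".

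Appendix H is the sample script for the call. It opens with "Thank you for joining me on this call. How are you doing today" and reaches the form only at the end: "You successfully replaced and paired your new Dexcom G6 PRO sensor. We will now finish this zoom call with a short survey".

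Appendix Q shows the form. The relevant question is "Have you experienced any problems with your glucose monitoring system (sensor or app", followed by a free-text field: "Insert notes for sensor problems, smartphone app problems, and adverse events".

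Elsewhere, section 3.13.2 (CGM application) has staff tell participants at the first application to report swelling, redness, bruising or bleeding. Section 3.7 describes daily texts on days 1 to 20 that check compliance and wellbeing.

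**The concern.** The call is the planned live contact between two 10-day wear periods, and local site reactions are the device effects that participants are told to watch for. It is also the only contact that the protocol expressly describes as asking about adverse events. If the question follows the new application, staff may learn of a reaction to sensor 1 only when sensor 2 is already in place. The plan would then collect the information but lose its use for the step it bears on most directly.

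The order matters more because the rest of the safety ascertainment is loosely specified. SAP section 6.3 relies on participant reports or occasional assessment, and neither schedule of assessments (Protocol section 3.8 and Appendix F) has an adverse-event row.

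**Working it through.** No arithmetic applies. The check sets the sections side by side.

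1. **Order of steps on the call.**
   - CGM Wear Phase names replacement first and inquiry second, without saying that one must precede the other.
   - G6 sensor replacement fixes when the form is completed: after replacement.
   - Appendix H gives the full sequence: greeting, willingness to continue, video, removal of sensor 1, application of sensor 2, transmitter, pairing, survey.
   - All three are consistent with the question coming last. The script is the one that settles it.

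2. **What the script asks before sensor 2 goes on.**
   - The opening question is a greeting. Its scripted reply assumes a good answer and has no branch for a problem.
   - After removal, the participant shows the removed sensor on screen, not the skin beneath it.
   - Staff then check the site chosen for the new sensor.
   - None of these steps is an adverse-event question. The pause after removal is a natural place for one.

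3. **What the form asks.**
   - The page shown has one general question on problems with the sensor or app, and one notes field that includes adverse events.
   - It does not name the four signs listed at baseline.
   - The problem question sits above the item confirming successful replacement but below the replacement date and new sensor code. The form's own layout therefore does not decide when the question is put.
   - Section 3.17.3 describes the contents of this form without mentioning an adverse-event item, whereas section 3.13.2 says that it covers AEs and SAEs.

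4. **Other routes by which a reaction could be known before day 10.**
   - Participants can report at any time (sections 3.13.2, 3.17.3 and 3.23). This depends on their coming forward.
   - Side effects are to be monitored at any interaction (section 3.15). No procedure or question is given.
   - The daily texts assess wellbeing according to section 3.7. Section 3.13.2 (CGM Wear Phase and Dietary logs) describes them as diet and video prompts with varying questions, and no adverse-event item is specified.
   - The satisfaction-survey items on irritation, bruising and pain (Appendix U) come at the post visit, after both wear periods.

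5. **When the PI and physician would hear.**
   - Section 3.23 has the coordinator tell the PI within 24 hours of a report.
   - Section 3.15 gives physician review of AEs within two workdays in one paragraph and four in another.
   - Either interval is longer than the call.

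The result is that there is no scripted adverse-event check between the start of the day-10 call and the second application, and no earlier contact has a defined adverse-event question.

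**The case against.** The strongest reply has four parts.

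- **Other channels exist.** A reader might infer that this is the only scheduled safety contact, or that a sensor 1 reaction is first raised on this call. The documents do not support that. Participants are told at baseline what to report, are texted daily about wellbeing, and can trigger a staff call and an adverse-event form at any time. This part stands. What remains is narrower: those channels have no defined adverse-event question.

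- **Completing a form is not the same as asking its questions.** The form is open throughout the call, and it cannot be finished earlier because it records the new sensor's code and whether replacement succeeded. This also stands as far as it goes. However, the script places the survey after pairing, and staff who follow it will ask then. The protocol calls the script an example, so practice may have differed.

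- **The form may ask more than is visible.** The sheet in Appendix Q is numbered page 3, and it does have an adverse-event notes field. The criticism of the item must therefore be confined to the page shown.

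- **An earlier question would not secure prior review.** Given the reporting intervals above, moving the question within the same call does not by itself bring the PI or physician in before sensor 2. That stands and limits the benefit. The staff member on the call would still know of the reaction before the new applicator is opened, which the present order prevents.

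The script also directs the second sensor to the other arm. That changes the site, not when the question is asked.

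**Conclusion.** The point holds as a matter of sequence. The explicit adverse-event question on the day-10 call follows application and pairing of sensor 2, and no scripted check precedes reapplication. This affects one question on one call for each participant taken through the script, with a target of 20. It rests on two assumptions: that calls follow Appendix H as written, and that the page in Appendix Q shows the relevant items.

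Two further inferences are tempting and should not be drawn. One is a count of participants given a second sensor despite an unreported reaction. The documents give no reaction rate and no rate of non-reporting, so no count can be derived, and zero is compatible with everything stated. The other is that sensor 1 events are under-recorded. No section shows this, and the post-visit survey provides a later prompt.

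The sections do not flatly contradict one another. They leave unsettled when and how adverse events are asked about. The change is worth making because it is specific and nearly free, but the gain is modest.

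**What to change.** In section 3.13.2 (G6 sensor replacement) and Appendix H, put the adverse-event item directly after sensor 1 is removed and before the new applicator is opened. Word it to name swelling, redness, bruising and bleeding. Leave the device items (replacement date, sensor code, confirmation of replacement) at the end.

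Reconcile section 3.7, the CGM Wear Phase, Dietary logs and G6 sensor replacement parts of section 3.13.2, and Appendix H, so that they agree on when adverse events are asked about. State whether the daily wellbeing text includes an adverse-event question. What follows a reported reaction stays with the PI and study physician; no clinical rule is proposed here.

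The cost is about a minute on the call before application, an edit to one script and one REDCap form, and notification of the IRB. No visit or staff member is added.

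Section 3.6 dates the final screening to 30 August 2024. Where the replacement calls are already complete, the change applies to follow-on studies that reuse these materials, and the G1 report should state that the structured adverse-event question followed reapplication.

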3.14 Concomitant Medication

Concomitant medication is not applicable with the Continuing Glucose Monitoring study.

3.15 Safety Reporting Guidelines

This section of the MOP details the definitions of and procedures for reporting AEs.

The Guidelines provide:

- *Definitions of AEs, serious AEs, and unanticipated problems*
- *Responsibilities of investigators*
- *Description of terms used in reporting.*

This section should delineate the AEs, as related to the study, serious AEs, and safety reporting procedures.

There is a potential for study participants to experience unexpected side effects. These side effects will be closely monitored by the study staff during any interaction involving the Continuous Glucose Monitoring (CGM) device or research protocol. The research coordinator will be readily available by phone in the event of a study-related participant emergency. If participant adverse events occur, the study physician will review adverse events (AEs) within two workdays and serious adverse events (SAEs) within two workdays, as well as treatment retention rates and reasons for active withdrawal. Safety information for this study will be reported to the study physician in an unblinded manner because the physician will not prepare nor analyze study data for analysis. All relevant information for each SAE, including event details and outcomes, concomitant medications, the subject's medical history, current conditions, and pertinent glucose data, will be reported to both the study physician and the Institutional Review Board (IRB) within two workdays. Subsequently, this information will undergo thorough review by the physician to determine its potential relevance to the study protocols. The physician will provide feedback about protocol alterations based on any relevant information generated from the comprehensive review of the adverse events.

There is a potential for study participants to experience unexpected side effects. These side effects will be closely monitored by the study staff during any interaction involving the CGM device or research protocol. The research coordinator will be readily available by phone in the event of a study-related participant emergency. If participant adverse events occur, the study physician will review adverse events (AEs) within four workdays and serious adverse events (SAEs) within two workdays, as well as treatment retention rates and reasons for active withdrawal. Safety information for this study will be reported to the study physician in an unblinded manner because the physician will not prepare nor analyze study data for analysis.

Reporting processes

All relevant information for each SAE, including event details and outcomes, concomitant medications, the subject's medical history, current conditions, and pertinent glucose data, will be reported to both the study physician and the Institutional Review Board (IRB) within two workdays. Subsequently, this information will undergo thorough review by the physician to determine its potential relevance to the study protocols. The physician will provide feedback about protocol alterations based on any relevant information generated from the comprehensive review of the adverse events.

3.16 Study Compliance

Protocol deviations include, but are not limited to the following:

- *Randomization of an ineligible participant*
- *Failure to obtain Informed Consent*
- *Enrollment of a participant into another study*
- *Failure to keep IRB approval up to date*
- *Wrong treatment administered to participant*

- *Outcome measurement not performed*

This section should describe what constitutes protocol deviations and the process for reporting such deviations to appropriate parties, including the study chair and site investigator, the Coordinating Center, NCCIH, and the DSMB or safety officer, within 24 hours of occurrence if possible, or as soon as they are discovered. Investigators need to follow their IRB requirements for reporting protocol deviations to the Board. In addition, if monitors discover any of these deviations during a site visit, they should list any such occurrence in their monitoring report. The Coordinating Center (for the study) and the study coordinator (for the site) should maintain a log of all protocol deviations and should report them routinely to the DSMB or safety officer. While there may be rational clinical reasons for an occasional deviation, a site with continuous problems is at risk for losing its funding. A log for recording protocol deviations should also be included in this section.

To track compliance from each participant of the study, the research coordinator will keep an up-to-date participant activity log. In this log, the coordinator will capture all phases completed and non completed from all participants that passed the prescreening phase. Each participant will be added in the Activity Log, as soon as they have prescreen passed and they have scheduled an initial visit. This log will be shared with the study's PI on a weekly basis. An example of the Participant Activity Log can be found in Appendix_K_.

